### **3. ENDPOINTS AND BASELINE VARIABLES: DEFINITIONS AND CONVENTIONS**

#### **3.1. Primary Endpoint(s)**

##### **3.1.1. Adverse Events**

An adverse event is considered a Treatment-Emergent Adverse Event (TEAE) if the event started during the effective duration of treatment. All events that start on or after the first

dosing day and time/start time, if collected, but before the end of the study will be flagged as TEAEs. The algorithm will not consider any events that started prior to the first dose date.

A 3-tier approach for summarizing AEs will not be used due to the low number of participants planned to be recruited.

Infusion site reactions are being assessed as part of AEs.

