1.3. Schedule of Activities

The SoA table provides an overview of the protocol visits and procedures. Refer to the [STUDY ASSESSMENTS AND PROCEDURES](#) section of the protocol for detailed information on each procedure and assessment required for compliance with the protocol.

The investigator may schedule visits (unplanned visits) in addition to those listed in the SoA table, in order to conduct evaluations or assessments required to protect the well-being of the participant.

PART 1: SAD (24-h infusion)

Visit Identifier	Screening Days -3 to 1	Day 1						End of Treatment Day 2	Follow-up 1 (Day 3)	Follow-up 2 (Day 6) ^k ±1 day Phone call where necessary	Follow-up 3 (Days 30-37) ^k Phone call where necessary	Early Termination
Planned Hours Post Start of Infusion		Pre-dose	0h	0.5h	2h	6h	12h	24h	48h			
ELIGIBILITY												
Informed consent	X											
Verify inclusion/exclusion criteria	X											
Demographics & Medical history	X											
Required Confinement		X	→	→	→	→	→	→	X			
PHYSICAL EXAMINATION & ECG & VITALS												
Complete physical examination	X							X				X
Targeted physical examination		X							X	X		
Supine Vital signs (temperature, pulse rate, blood pressure, respiratory rate)	X	X	X	X	X	X	X	X	X	X		X
Pulse oximetry/SpO ₂	X	X						X	X	X		X
Weight, Height	X											
12-Lead ECG ^a	X	X			X ^a	X ^a	X ^a	X	X			X
ECG Telemetry ^b	X	X	X	→	→	→	X					

Visit Identifier	Screening Days -3 to 1	Day 1						End of Treatment Day 2	Follow-up 1 (Day 3)	Follow-up 2 (Day 6) ^k ±1 day Phone call where necessary	Follow-up 3 (Days 30-37) ^k Phone call where necessary	Early Termination
Planned Hours Post Start of Infusion		Pre-dose	0h	0.5h	2h	6h	12h	24h	48h			
LABORATORY												
Hematology ^c	X	X				X		X	X	X		X
Blood chemistry ^c	X	X				X		X	X	X		X
Coagulation Panel (PT, aPTT, D-dimer) and Fibrinogen		X				X		X	X	X		X
Urinalysis ^c	X	X				X		X	X	X		X
FSH (post-menopausal females only) ^c	X											
Pregnancy test (WOCBP only)	X ^{c,d}									X ^d		
CCI [REDACTED]												
SARS-CoV-2 Viral load Assessments ^e	X	X				X		X	X	X		X
Plasma PD Biomarker Assessments ^g	X					X ^f		X	X	X		X
Serum PD Biomarker Assessments ^h	X					X ^f		X	X	X		X
Banked Biospecimen (Prep D1)	X					X ^f		X	X			X
Plasma Pharmacokinetics (PF-07304814 and PF-00835231)	X					X		X ⁱ	X			X
CCI [REDACTED]												
Urine Pharmacokinetics [REDACTED] (Cohort 2 only)		X ^j	X	→	→	→	→		X (36h)			
RANDOMIZATION												
STUDY INTERVENTION												

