3. OBJECTIVES, ESTIMANDS, AND ENDPOINTS

Objectives	Estimands	Endpoints
Primary:	Primary:	Primary:

To assess the safety and tolerability following single and multiple ascending doses of PF-07304814 in hospitalized participants with COVID-19.	N/A	
Frequency, severity, and causal relationship of TEAEs and withdrawals due to TEAEs (including infusion site reactions).Frequency and magnitude of abnormal laboratory findings.Changes from baseline in vital sign measurements, pulse oximetry/SpO₂, and 12-lead ECG parameters.
Secondary:	Secondary:	Secondary:

To evaluate the plasma PK of PF-07304814 and PF-00835231 and urinary PK of PF-00835231 following single ascending and multiple ascending doses in hospitalized participants with COVID-19.	N/A	Part 1: SAD 
PF-07304814 (prodrug) and PF-00835231 (active moiety) plasma PK: C₂₄ (end of infusion) and C₂₄ (dn).PF-00835231 urinary PK parameters: Ae, Ae%. Part 2: MAD 
PF-07304814 (prodrug) and PF-00835231 (active moiety) plasma PK: C₁₂₀ (end of infusion), C_{max}, C_{ss}, and t_{1/2}.
Tertiary/Exploratory:	Tertiary/Exploratory:	Tertiary/Exploratory:
■ [REDACTED]	C CI	■ [REDACTED]

Measurement of	N/A	
SARS-CoV-2 viral load (RT-PCR) and, if

Objectives	Estimands	Endpoints
SARS-CoV-2 viral load (by RT-PCR) and, if feasible, molecular analysis in nasopharyngeal swab and saliva samples over time.		feasible, molecular analysis in nasopharyngeal swab and saliva (at Screening, Days 1, 2, 3 and 6 for Part 1: SAD , and at Screening, Days 1, 3, 6, 7, 10, 14 and last follow-up for Part 2: MAD).

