8.3.1. Time Period and Frequency for Collecting AE and SAE Information

The time period for actively eliciting and collecting AEs and SAEs (“active collection period”) for each participant begins from the time the participant provides informed consent, which is obtained before the participant’s participation in the study (ie, before undergoing any study-related procedure and/or receiving study intervention), through and including a minimum of 28 calendar days, except as indicated below, after the last administration of the study intervention.

Follow-up by the investigator continues throughout and after the active collection period and until the AE or SAE or its sequelae resolve or stabilize at a level acceptable to the investigator and Pfizer concurs with that assessment.

For participants who are screen failures, the active collection period ends when screen failure status is determined.

If the participant withdraws from the study and also withdraws consent for the collection of future information, the active collection period ends when consent is withdrawn.

If a participant definitively discontinues or temporarily discontinues study intervention because of an AE or SAE, the AE or SAE must be recorded on the CRF and the SAE reported using the CT SAE Report Form.

Investigators are not obligated to actively seek AEs or SAEs after the participant has concluded study participation. However, if the investigator learns of any SAE, including a death, at any time after a participant has completed the study, and he/she considers the event to be reasonably related to the study intervention, the investigator must promptly report the SAE to Pfizer using the CT SAE Report Form.

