10.3.1. Definition of AE

AE Definition

• An AE is any untoward medical occurrence in a patient or clinical study participant, temporally associated with the use of study intervention, whether or not considered related to the study intervention.• NOTE: An AE can therefore be any unfavorable and unintended sign (including an abnormal laboratory finding), symptom, or disease (new or exacerbated) temporally associated with the use of study intervention.

Events Meeting the AE Definition

• Any abnormal laboratory test results (hematology, clinical chemistry, or urinalysis) or other safety assessments (eg, ECG, radiological scans, vital sign measurements), including those that worsen from baseline, considered clinically significant in the medical and scientific judgment of the investigator Any abnormal laboratory test results that meet any of the conditions below must be recorded as an AE:
• Is associated with accompanying symptoms.• Requires additional diagnostic testing or medical/surgical intervention.• Leads to a change in study dosing (outside of any protocol-specified dose adjustments) or discontinuation from the study, significant additional concomitant drug treatment, or other therapy.• Exacerbation of a chronic or intermittent preexisting condition including either an increase in frequency and/or intensity of the condition.• New conditions detected or diagnosed after study intervention administration even though it may have been present before the start of the study.• Signs, symptoms, or the clinical sequelae of a suspected drug-drug interaction.• Signs, symptoms, or the clinical sequelae of a suspected overdose of either study intervention or a concomitant medication. Overdose per se will not be reported as an AE/SAE unless it is an intentional overdose taken with possible suicidal/self-harming intent. Such overdoses should be reported regardless of sequelae.

Events NOT Meeting the AE Definition

- Any clinically significant abnormal laboratory findings or other abnormal safety assessments which are associated with the underlying disease, unless judged by the investigator to be more severe than expected for the participant's condition.
- The disease/disorder being studied or expected progression, signs, or symptoms of the disease/disorder being studied, unless more severe than expected for the participant's condition.

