- Medical or surgical procedure (eg, endoscopy, appendectomy): the condition that leads to the procedure is the AE.
- Situations in which an untoward medical occurrence did not occur (social and/or convenience admission to a hospital).
- Anticipated day-to-day fluctuations of preexisting disease(s) or condition(s) present or detected at the start of the study that do not worsen.

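### The start-date-only TEAE rule can leave out an adverse event that opens between consent and first dose and then worsens on study intervention

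*SAP*

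**What the plan says.** SAP 3.1.1 flags events by onset. Those starting on or after the first "dosing day and time/start time, if collected, but before the end of the study will be flagged as TEAEs", and it adds: "The algorithm will not consider any events that started prior to the first dose date". Nothing is said about a change in severity or seriousness after dosing. The protocol uses the term TEAE but does not define it. SAP 6.1.1 refers AE reporting to sponsor standards that are not part of the documents.

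The flag determines the first primary endpoint in Protocol Section 3, repeated in SAP 2.1: "Frequency, severity, and causal relationship of TEAEs and withdrawals due to TEAEs (including infusion site reactions").

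Three protocol provisions bear on which start date an event carries:

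- Section 8.3.1: active AE collection "begins from the time the participant provides informed consent". The Schedule of Activities places screening at "Screening Days -3 to 1".
- Section 10.3.1: events that count as AEs include "Exacerbation of a chronic or intermittent preexisting condition including either an increase in frequency and/or intensity of the condition".
- Section 10.3.3 (follow-up of AEs and SAEs): new information on an event goes on the CRF first completed for it. No text says that a change in severity or seriousness opens a new record.

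**The concern.** Participants are hospitalised with COVID-19, so some may already have an AE open when the infusion starts. If that event becomes severe or serious, or leads to stopping study intervention, a safety reader would expect to see it in the treatment-emergent tables. Under SAP 3.1.1 a record with a pre-dose start is excluded whatever happens next, and one flag governs frequency, severity and withdrawals together.

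The rule also differs from the rest of the primary safety analysis. SAP 3.1.2 takes baseline status into account for laboratory abnormalities, and SAP 3.1.3 to 3.1.5 assess vital signs, ECG and SpO2 by change from baseline. AEs alone are classified without regard to change from the pre-dose state.

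**Working it through.** The plan states no figure on this point, so there is none to reproduce. The check compares the provisions and then sizes a single loss.

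**Step 1: one clinical course, two ways to record it.** Take an AE that starts on Day -1 as mild, becomes severe on Day 3 of a Part 2 infusion, and ends treatment.

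| Recording | Start on the record | Flag under SAP 3.1.1 | In frequency, severity and withdrawal summaries? |
|---|---|---|---|
| Update to the original record (a natural reading of Protocol 10.3.3) | Day -1 | Not a TEAE | No, in none of the three |
| New AE for the exacerbation (as Protocol 10.3.1 allows) | Day 3 | TEAE | Yes, as severe |

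The same course is counted or not depending on a recording choice that neither document settles.

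**Step 2: which pre-dose illness is exposed.**

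- *Conditions present before consent (medical history).* Exacerbation is an AE in its own right. What Protocol 10.3.1 leaves out is "Anticipated day-to-day fluctuations of preexisting disease(s) or condition(s) present or detected at the start of the study that do not worsen". Post-dose worsening can carry a post-dose start and be flagged. Not exposed.
- *COVID-19 itself.* Protocol 10.3.1 does not count as an AE "The disease/disorder being studied or expected progression, signs, or symptoms of the disease/disorder being studied, unless more severe than expected". That exclusion comes from the AE definition, not from the TEAE rule. Not exposed.
- *AEs first recorded between consent and first dose.* These have a pre-dose start. Exposed if later worsening stays on the same record. The window is about 3 days at most and can be shorter.

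**Step 3: size of one loss.** Inputs: 6 active and 2 placebo per cohort (Protocol 9.2); placebo reported by cohort in Part 1 (SAP 6). If the lost event is the participant's only TEAE, incidence changes by 1/n:

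- active group of 6: 1/6 = 16.7 percentage points;
- Part 1 placebo group of 2: 1/2 = 50 percentage points.

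A participant with another TEAE stays in the incidence count, but the worst severity or the withdrawal can still be lost.

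**Step 4: how often it might arise (assumption only).** Let q be the share of participants with an exposed AE that worsens after dosing. The documents give no value for q, so a range is shown. The chance of at least one such participant among 6 active is 1 − (1 − q)^6. Full enrolment is (2 + 3 + 2 + 2) × 8 = 72, matching the protocol, of whom 9 × 6 = 54 are active; the expected number affected is 54q.

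| Assumed q | At least one of 6 active | Expected among 54 active |
|---|---|---|
| 2% | 11% | 1.1 |
| 5% | 26% | 2.7 |
| 10% | 47% | 5.4 |
| 20% | 74% | 10.8 |

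These are illustrations, not estimates of the undercount.

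**The case against.** The strongest reply is that the AE definition already handles worsening. Besides the clause on chronic or intermittent conditions, the note to the definition in Protocol 10.3.1 covers exacerbated as well as new disease, without that limit. Clinically significant results that worsen from baseline also count as AEs. If sites enter such worsening as a new event, the existing algorithm works. This stands in part: it rules out the reading that SAP 3.1.1 discards all on-drug worsening in ill patients. It does not close the gap, because allowing an exacerbation to be an AE is not an instruction to open a second record for an AE already on the CRF, and Protocol 10.3.3 points towards updating the first. The sponsor standards might settle it, but they cannot be assumed to reverse an explicit exclusion in the SAP.

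A reader might also infer that the rule biases the drug-placebo comparison towards no harm. The documents do not support that. The rule applies to both arms, and one lost participant shifts a 2-person placebo group more than a 6-person active group. What can be said is that, within an arm, the exclusion can only lower the count.

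Nor do the documents support a reading that patient protection is weakened. All AEs from consent are recorded, SAEs go to the sponsor within 24 hours (Protocol 8.3.1.1), and the escalation stopping rules in Protocol 6.6.1 use AEs, SAEs and abnormalities, not the TEAE flag. The other primary safety measures would also show some of the worsening. These points stand, and they limit the matter to how the primary endpoint is reported.

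**Conclusion.** Wrong as written, within a narrow scope. The stated algorithm excludes any AE record with a pre-dose start. An AE that opens between consent and first dose, and then worsens, becomes serious or leads to discontinuation, can be absent from all three TEAE summaries in the primary endpoint. This rests on one condition that the documents do not resolve: that the worsening is kept on the original record.

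The total undercount cannot be calculated. One lost participant is worth 16.7 points in a 6-person active group, or 50 points in a 2-person Part 1 placebo group, provided the lost event was that participant's only TEAE. With no hypothesis test or statistical decision rule (SAP 5.1), the consequence is an incomplete descriptive safety summary. In groups this small, one omitted severe or serious event would visibly change the table.

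**What to change.** Amend SAP 3.1.1 so that an AE starting before first dose is flagged as a TEAE if, after the start of dosing, it increases in severity, becomes serious or leads to discontinuation of study intervention. Tabulate it at its worst post-dose severity.

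Pair this with a recording rule in the CRF completion instructions: enter such worsening as a new AE with its own start date and time, or record the date of the severity change on the existing entry. Without one of these, the programmed flag has nothing to work from.

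SAP version 2.0 is dated after some cohorts were handled, so a new instruction may come too late for participants already treated. For them, list the AEs open at first dose and query the date of any worsening before database release.

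The cost is a short site instruction, some programming, possibly a few queries, and slightly higher reported TEAE counts. Design and sample size do not change. Because the flag determines a primary endpoint, the sponsor should also decide whether the change is a major modification that Protocol Section 9 requires to be reflected in an amendment.

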### **3.1.2. Laboratory Data**

Safety laboratory tests will be performed as described in the protocol.

Baseline will be the last pre-dose measurement.

To determine if there are any clinically significant laboratory abnormalities, the haematological, clinical chemistry (serum) and urinalysis safety tests will be assessed against the criteria specified in the sponsor reporting standards. The assessment will take into account whether each participant's baseline test result is within or outside the laboratory reference range for the particular laboratory parameter.

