- j. Administration starts on Day 1 and continues for 24 hours and ends on Day 2. **Sentinel dosing will be used in each dose-escalating cohort.** A small cohort of 2 participants (1 receiving PF-07304814 and 1 receiving placebo) will be dosed prior to the remainder of the cohort. All available safety and tolerability data from the 2 sentinel participants up to Day 3 at 24 hours post completion of dosing will be reviewed by the Investigator(s) (if available), the study team and IRC. The independent IRC will then determine whether it is safe to proceed to dose the remaining participants in the cohort.

k. For discharged participants, Days 6 and 30-37 should be conducted at the clinical site. However, if this is not possible, the visit may be conducted by phone in which case only clinical data (AE, **CCI** [REDACTED] concomitant medications) and contraception check will be obtained. (If available, kits to assess viral load to be provided for at-home specimen collection in the instance that a visit is conducted by telephone, and arrangements may be made to collect blood samples for clinical chemistry and/or hematology).

[REDACTED]

[REDACTED]

PART 2: MAD (120-h infusion)

Visit Identifier	Screening Days -3 to 1	Treatment Day 1	Treatment Days 2-5	End of Treatment Day 6	Follow-up 1 (Day 7)	Follow-up 2 (Day 10) ^l ±1 day	Follow-up 3 (Day 14) ^l ±2 days	Follow-up 4 (Day 34-41) ^l	Early Termination
Planned Hours Post Start of Infusion		pre-Dose	24h (Day 2), 48h (Day 3), 72h (Day 4), 96h (Day 5)	120h					
ELIGIBILITY									
Informed consent	X								
Verify inclusion/exclusion criteria ^a	X								
Demographics & Medical history	X								
Required Confinement		X	→	→	X				
PHYSICAL EXAMINATION & ECG & VITALS									
Complete physical examination	X			X					X
Targeted physical examination		X	X		X	X	X	X	
Supine vital signs (temperature, pulse rate, blood pressure, respiratory rate)	X	X	X	X	X	X	X	X	X
Pulse oximetry/SpO ₂	X	X	X	X	X	X	X	X	X
Weight, Height	X								
12-Lead ECG ^b	X	X	Day 2, 3, 5 only	X	X	X	X	X	X
LABORATORY									
Hematology ^c	X	X	Day 2, 3, 5 only	X	X	X	X	X	X
Blood chemistry ^c	X	X ^d	Day 2, 3, 5 only	X ^d	X	X	X	X	X
Coagulation Panel (PT, aPTT, D-dimer) and Fibrinogen		X	Day 2, 3, 5 only	X	X	X	X	X	X
Urinalysis ^c	X	X	Day 3 only	X	X	X	X	X	X
FSH (to confirm post-menopausal status)	X								
Pregnancy test (WOCBP only)	X ^{c,e}						X		
CCI									
SARS-CoV-2 Viral load Assessments ^f	X	X	Day 3 only	X	X	X	X	X	X

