2.2.2.1. Study C4611007 - Ongoing

This is the second clinical administration with PF-07304814, but first in healthy adult participants. This is a Phase 1, randomized, double-blind, sponsor open (ie, participant blind, investigator blind and sponsor open), placebo-controlled SAD study, with ongoing review of safety, tolerability, and PK.

There are 2 interleaving cohorts with a total of approximately 16 participants (approximately 8 participants in each cohort), with 2-period cross-over in each cohort. For each period, approximately 6 participants will have received a single dose of PF-07304814 administered as a 24h continuous IV infusion, and approximately 2 participants will have received placebo. Each participant may have received either a single dose of PF-07304814 or a placebo during each period.

The nominal doses of PF-07304814 are 50 mg, 150 mg, 500 mg, and 700 mg for a 24h continuous infusion. In addition to standard safety assessments, hsCRP, D-dimer, and coagulation panel (aPTT, PTT) are monitored to evaluate any potential pro-inflammatory or hypercoagulable effect of study intervention.

The study began in October 2020, and at the time of the data cutoff date 21 November 2020, safety data from last planned safety labs (Day 5) from the last participant was reviewed. There were 20 TEAEs reported by 12 participants. All of the TEAEs were categorized as mild in severity. One AE of injection site pain, reported as mild in severity, was considered treatment related by the investigator. For the description of each AEs please refer to the IB (December 2020). There were no deaths, serious AEs (SAEs), severe AEs, or discontinuations due to AEs during the study.

There were no individual laboratory abnormalities assessed as clinically significant by the investigator. Across the treatment groups there were no clinically significant changes in the inflammatory marker, hs-CRP. Tests evaluating the coagulation system, aPTT, PT, fibrinogen and D-dimer, were similarly without clinically significant changes over time. No participant developed a value that was clinically significantly elevated or outside the normal range. Overall, there was no evidence of a pro-inflammatory effect clinically or based on laboratory results, at all dose levels.

Preliminary pharmacokinetic (PK) data following single dose 24h continuous IV infusion at 50, 150, 500 and 700 mg are included in this update with a data cut-off date of 21 November 2020.

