10.2. Appendix 2: Clinical Laboratory Tests

The following safety laboratory tests will be performed at times defined in the **SoA** section of this protocol. Additional laboratory results may be reported on these samples as a result of the method of analysis or the type of analyzer used by the clinical laboratory, or as derived from calculated values. These additional tests would not require additional collection of blood. Unscheduled clinical laboratory measurements may be obtained at any time during the study to assess any perceived safety issues.

Table 10. Protocol-Required Safety Laboratory Assessments

Hematology	Chemistry	Urinalysis	Other
Hemoglobin	BUN	pH	At screening only:
Hematocrit	serum creatinine (and eGFR using Cockcroft-Gault)	Glucose (qual)	
 • FSH^b • Pregnancy test (β-hCG)^c
RBC count		Protein (qual)	
MCV		Blood (qual)	
MCH	Glucose	Ketones	At timepoints in SoA:
MCHC	Calcium	Nitrites	
 • Coagulation 
 • D-dimer • PT/INR • aPTT • Fibrinogen
Platelet count	Sodium	Leukocyte esterase	
WBC count	Potassium	Urobilinogen	
Total neutrophils (Abs)	Chloride	Urine bilirubin	
Eosinophils (Abs)	Total	Microscopy ^a	
Monocytes (Abs)	CO ₂ (bicarbonate)		
Basophils (Abs)	AST, ALT		
Lymphocytes (Abs)	Phosphorus		
	Total bilirubin		
	Alkaline phosphatase		
	Uric acid		
	Albumin		
	Total protein		
	Lipid panel (Part 2 only)		

- a. Only if urine dipstick is positive for blood, protein, nitrites, or leukocyte esterase.
- b. For confirmation of postmenopausal status only.
- c. Local urine testing will be standard for the protocol unless serum testing is required by local regulation or IRB/EC. Serum or urine β -hCG for female participants of childbearing potential.

Investigators must document their review of each laboratory safety report.

10.3. Appendix 3: Adverse Events: Definitions and Procedures for Recording, Evaluating, Follow-up, and Reporting

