#### 3.3.2. Biomarkers

Exploratory biomarkers will be collected according to the SoA given in the protocol.

Baseline will be the last pre-dose measurement.

The following biomarker endpoints will be determined:

- Change from baseline in blood hs-CRP, LDH, Ferritin, WBC, Monocytes, Haptoglobin, Procalcitonin, Neutrophils and Creatine Kinase
- Change from baseline in coagulation markers D-dimer, PT, aPTT and Fibrinogen
- Change from baseline in cytokines of inflammatory response

Reactive and Non-Reactive IgG will be collected according to the SoA given in the protocol.

All other exploratory biomarkers will be used for internal exploratory purposes and will not be included in the CSR but reported in a separate addendum.

CCI

CCI

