#### **6.3.2. Biomarkers**

Absolute and changes from baseline in blood hs-CRP, LDH, Ferritin, WBC, Monocytes, Haptoglobin, Procalcitonin, Neutrophils and Creatine Kinase will be summarized by treatment and time post-dose. Baseline is as defined in [Section 3.3.2](#).

Absolute and changes from baseline in coagulation markers (D-dimer, PT, aPTT) and Fibrinogen will be summarized by treatment and time post-dose. Baseline is as defined in [Section 3.3.2](#).

Absolute and changes from baseline in cytokines of inflammatory response will be summarized by treatment and time post-dose. Baseline is as defined in [Section 3.3.2](#).

Individual and mean changes from baseline plots will be produced by treatment. For cytokines - individual absolute plots will also be produced.

The percentage of participants with Reactive and Non-Reactive IgG will be summarized by treatment.

Listings of biomarkers, coagulation markers, cytokines and serology will be produced separately to the laboratory listing.

CCI

A series of black redaction bars of varying lengths, starting with a short one under 'CCI' and continuing with longer ones below it, ending with a very long one at the bottom.

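### SAP 3.1.2 leaves the protocol's safety coagulation panel out of the laboratory abnormality assessment, so the primary laboratory endpoint has no stated frequency of abnormal coagulation results

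*SAP*

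**What the plan says.** Protocol Section 3 lists, among the primary safety endpoints, "Frequency and magnitude of abnormal laboratory findings". No class of laboratory test is excluded.

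Protocol Appendix 2 defines the safety tests in a table headed "Protocol-Required Safety Laboratory Assessments" (Table 10). Its columns are hematology, chemistry, urinalysis and a fourth, mixed column. That column holds the screening-only tests and a coagulation group taken at the scheduled visits: D-dimer, PT/INR, aPTT and fibrinogen. Both Schedules of Activities in Section 1.3 carry a laboratory row, "Coagulation Panel (PT, aPTT, D-dimer) and Fibrinogen", separate from the plasma and serum PD biomarker rows.

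The protocol also gives the same tests an exploratory role, in the exploratory endpoints of Section 3 and under plasma PD biomarkers in Section 8.8.5.1.

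For the primary laboratory endpoint, SAP 3.1.2 states that "the haematological, clinical chemistry (serum) and urinalysis safety tests will be assessed against the criteria specified in the sponsor reporting standards", taking account of whether each baseline result was inside or outside the reference range. SAP 6.1.2 lists and summarizes laboratory data under the sponsor reporting standards and adds a by-participant listing of the most clinically significant abnormalities.

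For coagulation, SAP 3.3.2 defines "Change from baseline in coagulation markers D-dimer, PT, aPTT and Fibrinogen". SAP 6.3.2 adds absolute values and plots, and says: "Listings of biomarkers, coagulation markers, cytokines and serology will be produced separately to the laboratory listing".

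**The concern.** The protocol gives coagulation two roles, safety panel and exploratory marker. The SAP spells out only the second. The frequency part of the primary laboratory endpoint is therefore specified for three panels and unstated for the fourth.

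The omitted panel bears on a risk that the current protocol text takes seriously. Section 2.2 describes hospitalized COVID-19 patients as prone to hypercoagulability and thromboembolic events. Section 5.2 excludes people with prior venous thromboembolism and women on hormonal therapy. In the companion healthy-volunteer study, Section 2.2.2.1 notes that hsCRP, D-dimer and the "coagulation panel (aPTT, PTT) are monitored to evaluate any potential pro-inflammatory or hypercoagulable effect of study intervention". As background only, the log entry for Amendment 3 records thrombotic events as an added risk of study intervention.

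At stake is a comparison of active with placebo, by dose, of how many participants developed an abnormal coagulation result given where they started. With about six active participants per cohort, a mean change is a weak summary of such shifts. A count against stated criteria is the direct answer to an endpoint worded as a frequency.

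**Working it through.** No power, alpha or sample size figure bears on this point, and the plan gives no figure to reproduce. The check compares the texts and counts scheduled draws.

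**1. Panels.** These are the repeated safety panels in Protocol Table 10 and their treatment in the SAP:

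| Table 10 panel | Named in SAP 3.1.2 for abnormality criteria | Other stated SAP output |
|---|---|---|
| Hematology (includes platelets) | Yes | WBC, monocytes and neutrophils also shown as biomarkers |
| Chemistry | Yes | – |
| Urinalysis | Yes | – |
| Coagulation | No | Absolute values, change from baseline, plots, separate listing |

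Three of the four panels are named; coagulation is the one left out.

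**2. Is the gap filled elsewhere in the SAP?** Appendix 1 has categories for ECG, vital signs and pulse oximetry only. Sections 3.3.2 and 6.3.2 contain no abnormality criterion. INR, which Table 10 lists with PT, does not appear in the readable SAP text. No stated output gives a frequency of abnormal coagulation results.

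**3. Does the exploratory role explain the omission?** No. WBC, monocytes and neutrophils are also biomarkers in SAP 3.3.2, yet they stay in the abnormality assessment because they are haematology tests. Being a biomarker does not remove a test from safety reporting. The gap comes from the three-class wording of 3.1.2.

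**4. Does adverse event reporting replace the count?** Only in part. A clinical DVT or PE would be a TEAE. But Protocol 8.2.4 and 10.3.1 do not treat laboratory abnormalities associated with the underlying disease as clinically significant findings or as AEs, unless they are worse than expected for the participant. An investigator could properly attribute a raised D-dimer to COVID-19 and record no event. A baseline-adjusted count by treatment does not depend on that attribution.

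**5. Data available.** From the coagulation row of each Schedule of Activities, leaving out early termination:

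- Part 1, after the start of infusion: 6h, 24h, 48h, Day 6 = 4 draws. With 4 tests, 4 × 4 = 16 results per participant.
- Part 2, after the start of infusion: Days 2, 3, 5, 6, 7, 10, 14 and 34–41 = 8 draws. With 4 tests, 4 × 8 = 32 results per participant.
- Both parts have a pre-dose draw, so baseline status can be determined.

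**6. Scale of one case.** In a cohort with 6 active participants, one newly abnormal participant is 1/6 = 17% in an abnormality table. This illustrates the resolution of such a table and is not a predicted effect.

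**The case against.** The strongest reply is that little information is lost. SAP 6.3.2 specifies individual as well as mean change-from-baseline plots, together with coagulation listings, and SAP 5.2.1 requires the median, minimum and maximum. At this cohort size an outlier would be visible. That stands: the values are shown. They are not counted against criteria, and the endpoint asks for a frequency.

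A second reply is that SAP 3.1.2 and 6.1.2 both defer to sponsor reporting standards, which may group coagulation with haematology. This cannot be checked. Table 10 and the separate coagulation listing in SAP 6.3.2 point the other way, but they do not settle it.

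Third, the listing in SAP 6.1.2 is not restricted by class in its own words. That is correct, so exclusion of coagulation from that listing is only an inference from 3.1.2. The companion study also reported no clinically significant coagulation changes (Protocol 2.2.2.1). That is reassuring, but it comes from healthy volunteers given 24-hour infusions.

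A reader might infer more than the documents support, in three ways:

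- That the SAP demoted coagulation to an exploratory measure. The protocol itself already gives it that role; the SAP repeats it and leaves the safety role unstated.
- That the trial has no count bearing on thrombosis. Clinical events are counted as TEAEs, and platelets are assessed under hematology.
- That dose-escalation review ignored coagulation. The stopping criterion in Protocol 6.6.1 covers clinically significant laboratory abnormalities without limiting the class.

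**Conclusion.** The point holds in a limited form. As written, SAP 3.1.2 omits one of the four repeated safety panels in Protocol Table 10 from the abnormality assessment, and no other SAP section supplies a coagulation abnormality frequency. The primary laboratory endpoint is therefore incompletely specified for four tests. What is missing is the baseline-adjusted count by treatment, not thrombotic safety information as a whole.

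The study is descriptive and tests no hypothesis, so no formal conclusion changes. Severity is minor to moderate. Confidence is moderate, because the conclusion assumes that the sponsor reporting standards do not already bring coagulation under one of the three named classes.

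**What to change.** In SAP 3.1.2 and 6.1.2, add D-dimer, PT/INR, aPTT and fibrinogen to the tests assessed against abnormality criteria by baseline status, on the Safety set, with counts by treatment. State that the listing of most clinically significant abnormalities includes them. If the sponsor reporting standards have no criterion for one of these tests, write one into the SAP, for example relative to the laboratory reference range and baseline. If the standards already cover the panel, one sentence saying so is enough. Keep the exploratory displays as they are.

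The cost is a few added table rows and possibly a criterion to define; no new samples or visits are needed. Many COVID-19 patients can be expected to be abnormal at baseline, which will make the counts harder to read. The baseline-status rule in SAP 3.1.2 is meant for that situation, provided the criteria for these tests are written to use it.
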